### ***H. Protocol Modifications & Deviations***

Changes to the written Protocol must be approved by the Sponsor unless the change is made to assure the safety of the subject. Written approval by the PI's IRB will be obtained by the Sponsor prior to implementation of the amendment.

Deviations from the protocol will be recorded in the Protocol Deviation Log and submitted to the Sponsor and IRB as required by local regulations.

## XVII. RISKS

The participant population for whom nanOss Bioactive 3D is intended is characterized by the inclusion and exclusion criteria and as described in the product labeling.

### ***A. Risks Associated with Instrumented PLF Surgery***

As with any operation, there are potential risks associated with spinal fusions and associated instrumentation.

Some of the most common complications following posterior lumbar fusion include:

- Adverse reactions to anesthesia
- Thrombophlebitis
- Infection
- Nerve damage
- Problems with bone graft
- Instrumentation/hardware problems (migration, fracture, failure, loosening)
- Muscle disruption
- Nonunion/delayed union
- On-going pain

Other less frequent complications may include:

- Adjacent segment disease
- Bowel or bladder incontinence
- Corrosion of metal hardware
- Damage to lymphatic vessels and/or lymphatic fluid exudation
- Death
- Deep infection
- Device component fracture
- Epidural hematoma, dural tear
- Fracture of the pedicle or vertebral bone
- Hardware migration
- Hematoma or seroma at the implant site
- Hemorrhage
- Ileus
- Loss of bladder or bowel control
- Loss of fixation
- Muscle damage
- Nerve root injury
- Pain, infection or weakness from bone harvest location
- Pneumonia, bronchopneumonia or collapsed lung
- Pulmonary or systemic embolism
- Secondary surgery to remove hardware
- Stress shield bone
- Thrombosis
- Vascular injury or damage resulting in catastrophic or fatal bleeding
- Wound dehiscence

These lists describe the most common risks that could occur with this kind of surgery. There may be other risks that are not currently known.

***B. Risks Associated with nanOss Bioactive 3D***

The primary risk associated with nanOss Bioactive 3D is the lack of a solid fusion. There may be other risks that are not currently known. Risks associated with bone void fillers include:

- Hematoma
- Site drainage
- Bone fracture
- Infection
- Fracture or extrusion of the bone void filler
- Deformity of the bone at the site
- Incomplete or lack of osseous bone ingrowth
- Continued pain
- Allergic reaction - nanoss Bioactive 3D contains a porcine (pig) collagen product which is sterilized as part of the manufacturing process
- Revision surgery

***C. Loss of Confidentiality***

The Sponsor and Study Sites will put forth best efforts to make sure personal information from medical records is kept private. However, personal information may be given out if required by law. Organizations that may look at and/or copy medical records for research, quality assurance, and data analysis include IRBs, the Sponsor and/or the FDA.

If information from the Study is published or presented at scientific meetings, a participant's name and other personal information will not be used.

***D. Risks Associated with the Lumbar CT Scan***

CT scans involve the risks of radiation. Having a CT scan may mean some added discomfort to the participant, specifically, feelings of claustrophobia when placed inside the CT scanner, or by lying in one position for a long time.

***E. Reproductive Risks***

Pregnant women may not participate in the Study because the risks to an unborn baby are unknown. A pregnancy test will be given prior to surgery to confirm the participant is not pregnant.

Women of child-bearing potential should not become pregnant while participating in the Study. Female participants able to become pregnant are responsible for using an effective birth control method such as birth control pills, barrier method (condoms, diaphragm, and cervical cap), intrauterine device (IUD), hormone implants or surgical sterility while taking part in the Study.

A participant that thinks she has become pregnant during the Study must tell the PI or Study personnel immediately.

#### ***F. Unknown Risks***

There may be other risks that are not currently known.

#### ***G. Minimization of the Risk***

Risks to the patients who have agreed to participate in the Study will be minimized to the extent possible in several ways. The PI, Sub-Investigator and Study personnel participating in the Study will be trained to select the appropriate patient. Patient selection is of paramount importance; the inclusion and exclusion criteria have been carefully chosen to describe the best patient for the procedure. The PI and Sub-Investigator must demonstrate that they have had appropriate training/experience with nanOss Bioactive 3D as well as the anticipated complications associated with nanOss Bioactive 3D. The Sponsor will assure appropriate training for each PI and Sub-Investigator prior to initiation of the Study at each site.

A unique identification number is assigned to each participant. This number will be used on any material transferred out of the Study Site.

The PI will closely monitor for complications and adverse events and record them on the appropriate case report forms. The Sponsor will investigate any report of an unanticipated adverse event. If an unreasonable risk occurs, the Sponsor will terminate the Study.

#### ***H. Justification for Study***

Low back pain impacts the lifestyle of many individuals and results in a diminished quality of life. There are no immediate benefit to participants, however, future participants may benefit from the information obtained in the Study. The Sponsor believes that the risk to the participant is justified.

#### ***I. Participant Benefit***

There are no direct benefits for a Study participant. The information from the Study will help doctors and the Sponsor learn more about the use of nanOss Bioactive 3D in spinal fusion procedures and could help future patients with similar conditions.

***J. Participant Costs***

Since this is a Study is in line with standard of care and using the product according to its FDA cleared indications and cleared labeling, the Sponsor will not provide any products free of charge. The surgical facility/institution/Study Site is responsible for purchasing products through normal purchasing channels.

The surgical facility/institution/Study Site is responsible for submitting claims to third party payers (e.g. Medicare, insurance carriers, etc.), in accordance with all applicable laws and guidelines for such third party payers, all procedure, radiologic, or other expenses incurred in performance of the Study.

***K. Participant Research Related Injury***

If a participant experiences a complication from participation in the Study, then the participant may be treated for it at the surgical facility/institution/Study Site. The surgical facility/institution/Study Site is responsible for submitting claims to third party payers (e.g. Medicare, insurance carriers, etc.), in accordance with all applicable laws and guidelines for such third party payers, for the reasonable and necessary items and services to diagnose and treat the complication.

## XVIII. PARTICIPANT ALTERNATIVES

Participants may receive the surgery and any of the products without having to participate in the Study.

### *A. Non-Operative Alternatives*

Treatment of back pain without surgery may include the following:

- Physical therapy.
- Facet joint injections.
- Epidural steroid injections.
- Acupuncture.
- Back school.
- Behavior modifications.
- Ultrasound.
- Hot or cold compresses.
- Anti-inflammatory medications.
- Analgesic medications.
- Muscle relaxers.
- Corsets or braces.

### *B. Operative Alternatives*

Treatment of back pain with surgery may include the following:

- Discectomy.
- Foraminotomy.
- Laminectomy.
- Laminotomy.
- Intradiscal electrothermal therapy (IDET).
- Intervertebral disc replacement surgery.

## XIX. STATISTICAL METHODS

### ***A. Primary Endpoint***

The primary endpoint includes successful fusion of the treated segment(s) 12 months postoperatively based on the quantitative and qualitative assessments of the x-rays and CT scan. Fusion is defined as:

1. Presence of bridging trabecular bone [i.e. presence of left posterolateral bridging AND/OR right posterolateral bridging], **AND**
2. Angular motion < 5°, **AND**
3. Translational motion < 3 mm

The sample size and percentage of treated segments successfully fused will be presented. Sample sizes and percentages of treated segments successfully fused will be presented for different groups based on smoking status, age, sex, BMI, the number of segments treated and whether or not an IBF device was used.

Non-fusion will be defined as the failure to meet any one of the above criteria for fusion.

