### B. *Objective*

The objective of the Study is to gather information about fusion results, clinical & radiographic outcomes, complications/adverse events and patient reported outcomes in patients treated with nanOss Bioactive 3D mixed with autograft bone and BMA. The results of nanOss Bioactive 3D will be compared to those cited in literature.

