## XI. STUDY DESIGN

### A. Study Type

This is a prospective, non-randomized and un-controlled post-market Study.

This is not an investigational treatment Study. nanOss Bioactive 3D is being studied in accordance with its cleared indications and cleared labeling. All participants will receive nanOss Bioactive 3D mixed with BMA and autograft in their posterolateral spine as part of their routine instrumented PLF surgery.

Clinic procedures will be related to standard of care for persons receiving treatment for posterior lumbar fusion surgery. Information from clinical notes, examinations, questionnaires, results of diagnostic tools, radiographs, tests and exams will be recorded for the Study at the following timepoints:

- Pre-Operative
- Surgery
- Discharge
- 6 Months Post-Operative
- 12 Months Post-Operative
- 24 Months Post-Operative

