#### ***D. Inclusion Criteria***

The participant must exhibit all of the following:

1. Is at least 21 years of age and is skeletally mature.
2. Has symptomatic spinal stenosis secondary to DDD with up to Grade 1 spondylolisthesis at one or two adjacent segments from L2-S1 requiring bilateral, instrumented PLF surgery.
3. Has completed a minimum of 6 months of non-operative treatment or has the presence of progressive symptoms or signs of nerve root/spinal cord compression and fusion is clinically necessary.
4. Has pre-operative objective evidence of primary diagnosis confirmed by appropriate imaging studies (AP/Lateral/Flexion/Extension x-rays & an MRI or CT scan).
5. Is willing and able to return for post-treatment exams according to the follow-up called for in the protocol.
6. Is able to review, understand and sign the informed consent document.

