## XIII. METHODS

### ***A. Schedule of Events***

Pre-operative, operative, discharge and post-operative follow-up data will be collected on all participants. The complete list of events is a supplemental document. A summary of the events is below.

Procedures	Pre-Op	Surgery	Discharge	6 Months +/- 4 weeks	12 Months + 8 weeks	24 Months + 8 weeks
Informed Consent & Eligibility Review	X					
Preoperative History & Physical	X					
Clinical & Neurological Evaluation	X		X	X	X	X
Surgery		X				
Discharge			X			
PI Radiological Assessment				X	X	X
Disposition						X
Routine X-rays (4 views)	X			X	X	X
Thin-slice (<math>\leq</math> 1.25 mm) lumbar CT scan w/o contrast with coronal and sagittal mpr					X	X*
Participant Forms (4)	X			X	X	X

\* = If clinically indicated, participants will complete a lumbar CT scan without contrast (e.g., PI determines there is a clinical need or the independent radiologist observed no posterolateral bridging bone in the 12 month CT).

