### **3. nanOss Bioactive 3D**

nanOss Bioactive 3D will be placed on top of the bed of autograft bone spanning the transverse-processes of the treated segment bilaterally.

- 10 cc of nanOss Bioactive 3D should be used for each segment treated (5cc/side).
- The amount of nanOss Bioactive 3D placed on each side of the posterolateral spine will be recorded.
- Equivalent amounts of nanOss Bioactive 3D placed bilaterally (see description and images below).
  - Single segment procedure options following rehydration:
    - A 5cc (25x50x4 mm) nanOss Bioactive 3D strip may be applied to each side of the treated segment (2 strips).
    - A 10cc (25x50x8 mm) nanOss Bioactive 3D strip may be cut in half lengthwise and applied bilaterally at the treated segment (1 strip).
    - A 10cc (25x100x4 mm) nanOss Bioactive 3D strip may be cut in half and applied bilaterally at the treated segment (1 strip).
  - Two segment procedure options following rehydration:
    - A 5cc (25x50x4 mm) nanOss Bioactive 3D strip may be applied to each side of each segment (4 strips).
    - A 10cc (25x50x8 mm) nanOss Bioactive 3D strip may be cut in half lengthwise and applied bilaterally, spanning both segments on each side (2 strips).
    - A 10cc (25x100x4 mm) nanOss Bioactive 3D strip may be applied to each side spanning both segments on each side (2 strips).
    - A 20cc (25x100x8 mm) nanOss Bioactive 3D strip may be cut in half lengthwise and applied bilaterally, spanning both segments on each side (1 strip).

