### ***B. Secondary Endpoints***

An assessment of secondary endpoints will include an analysis of the following to determine trends in the data;

1. Assessment of fusion 6 and 24 months postoperatively.
2. Pain score improvement using the VAS.
3. Physical disability score improvement using the ODI.
4. Physical-functioning improvement using the 36-Item HS.
5. Satisfaction with procedure.
6. No serious adverse event classified as related to nanOss Bioactive 3D or no device failure or subsequent intervention, excluding the removal of fixation after a solid fusion occurred.

The following additional data will be presented:

- The sample size and percentage of successfully fused segments 6 and 24 months postoperatively.
- Sample sizes and percentages of successfully fused segments for different groups based on smoking status, age, sex, BMI, the number of segments treated and whether or not an IBF device was used 24 months postoperatively.
- Demographic information will be presented as sample sizes and percentages.
- Satisfaction with procedure will be presented as sample sizes and percentages for each visit.

- Pain, physical disability and physical-functioning scores will be presented as sample sizes, means, standard deviations and ranges for each visit. The post-operative results will be compared to baseline levels.
- The proportion of clinical complications, reoperations, revisions, as well as unexpected adverse events will be calculated.

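### The 12-month fusion percentage, and the 6- and 24-month rates, should carry a 95% confidence interval clustered by participant, because they are to be set beside literature rates

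*Combined protocol and SAP*

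**What the plan says.** Section XIX.A defines fusion at 12 months per treated segment and describes the analysis in one sentence: "The sample size and percentage of treated segments successfully fused will be presented". Breakdowns by smoking status, age, sex, BMI, number of segments and interbody device use take the same form. Section XIX.B plans "The sample size and percentage of successfully fused segments 6 and 24 months postoperatively", and lists the breakdowns again for "the number of segments treated and whether or not an IBF device was used 24 months postoperatively", with none listed at 6 months. Pain, disability and function scores get means, standard deviations and ranges. Nowhere does the document plan a confidence interval, standard error, test or reference rate for fusion.

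Section XI.A states the design: "This is a prospective, non-randomized and un-controlled post-market Study". Section X.B names fusion results among what is gathered and adds: "The results of nanOss Bioactive 3D will be compared to those cited in literature". Participants qualify with disease "at one or two adjacent segments from L2-S1 requiring bilateral, instrumented PLF surgery" (XII.D, item 2), so one person contributes one or two segments to the percentage. Section XIII.C.3 allows a single graft strip on each side to cover both segments. Section XII.C expects 50 participants, and XII.B caps enrolment at 60.

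**The concern.** In a study without a control arm, published rates are the only outside yardstick. A percentage from about 50 participants, placed beside a published percentage with no statement of precision, does not show whether a gap between them exceeds sampling error.

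A reader could rebuild an approximate interval from the reported n and percentage, but that interval would treat segments as independent. Two adjacent segments share a patient, an operation and sometimes a strip, so their outcomes may well be correlated. The planned tables do not show how failures pair within participants, so a reader could not make the correction. The sponsor, who holds the participant-level data, can.

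**Working it through.** **Nothing to reproduce.** The document gives no sample-size calculation, significance level, expected fusion rate or reference rate.

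**Inputs.** From the documents: 50 expected participants (XII.C), a cap of 60 (XII.B), and one or two segments each (XII.D). Assumed: all 50 evaluable; 40% with two segments, so 30 one-segment and 20 two-segment participants and 30 + 2 × 20 = 70 segments; within-participant correlation ρ of 0.2 to 0.6; fusion rate p of 70%, 80% or 90%.

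**Design effect.** DEFF = [n1 + 2·n2·(1 + ρ)] / S, with effective n = S / DEFF.
- ρ = 0.2: (30 + 40 × 1.2)/70 = 1.114, effective n 62.8
- ρ = 0.6: (30 + 40 × 1.6)/70 = 1.343, effective n 52.1

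**Half-width** = 1.96 × √[p(1 − p)/effective n]. For example, at p = 0.8 and ρ = 0.2: 1.96 × √(0.16/62.8) = 9.9 points.

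| Fused | Independent (n = 70) | ρ = 0.2 | ρ = 0.6 | Added by clustering |
|---|---|---|---|---|
| 70% | 10.7 | 11.3 | 12.4 | 0.6–1.7 |
| 80% | 9.4 | 9.9 | 10.9 | 0.5–1.5 |
| 90% | 7.0 | 7.4 | 8.1 | 0.4–1.1 |

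The Wilson interval at the effective n, for 80% fused, is 68.5–88.0% (ρ = 0.2) or 67.3–88.6% (ρ = 0.6).

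**Other assumptions, at 80% fused, ρ from 0.2 to 0.6.** 60 participants: 9.0–9.9 points. 40 evaluable: 11.1–12.1. 20% two-segment: 10.5–11.1. 60% two-segment: 9.4–10.6.

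**Can a reader recover the correlation?** Take 32 of 40 segments fused among the 20 two-segment participants. The 8 failures may lie in 4 participants (both segments fused in 16/20 = 0.80) or in 8 (12/20 = 0.60). With ρ = (proportion with both fused − 0.64)/0.16, that allows anything from −0.25 to 1. The planned breakdown by number of segments does not settle it.

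**Coverage of nominal 95% intervals** (simulation on the base case, 200,000 trials per cell for ρ = 0.2 and 0.6; re-runs differ by about 0.1 point), at 70 / 80 / 90% fused:

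| Interval | ρ = 0 | ρ = 0.2 | ρ = 0.6 |
|---|---|---|---|
| Wald from n and % | 94.4 / 94.0 / 92.0 | 93.0 / 92.5 / 90.5 | 90.1 / 89.6 / 87.2 |
| Wilson from n and % | – | 93.8 / 93.6 / 91.6 | 90.9 / 90.8 / 88.4 |
| Wald, participant-robust variance | – | 93.9 / 93.2 / 91.3 | 93.6 / 92.4 / 90.2 |
| Wilson at n / estimated DEFF, floor 1, with G/(G − 1) | – | 95.1 / 95.0 / 94.3 | 94.8 / 94.6 / 93.8 |

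G is the number of participants. Without the G/(G − 1) factor, the last method covers 92.5% instead of 93.8% at 90% fused and ρ = 0.6.

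**The case against.** The strongest reply is that the study is descriptive. It sets out to gather information, and no hypothesis, margin or decision rests on the percentage. The literature comparison is one sentence in X.B, with no method and no reference rate, and XIX does not take it up. The sample size is printed beside every percentage, so rough precision can be recovered. All of this is true. It limits the weight of the point but does not remove it: a comparison is still planned, and an interval needs no hypothesis.

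Three stronger readings are tempting, and the documents do not support them.

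- A reader might infer that the primary result is invalid or that some figure is wrong. The segment percentage is a legitimate estimate, and nothing stated is contradicted.
- A reader might blame clustering for the whole 87–93% coverage of the simple Wald interval. Part of the shortfall belongs to the Wald method, which covers only 92.0–94.4% at zero correlation. The Wilson interval from the same n and percentage covers 88–94% at the assumed correlations.
- A reader might take the statement in XII.B that smokers are analysed separately to mean that up to 15 people leave the main estimate, which would widen the interval. XIX.A lists smoking status as one breakdown among several, which fits smokers staying in the overall figure.

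It also stands that an interval expresses sampling error only. It does not repair differences from published series in fusion definition, imaging or case mix.

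**Conclusion.** The point holds as a reporting gap in the primary result that should be closed. Every fusion percentage is planned without a measure of uncertainty, although an uncontrolled result is to be set beside published rates. On the base-case assumptions the omitted 95% half-width is about 7 to 12 points. The absent interval is the substance; the clustering correction is a refinement. The fusion rate, two-segment share and correlation are all assumptions, and the size moves with them, but at 80% fused every variation tried gave a half-width between 9.0 and 12.1 points.

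**What to change.** In XIX.A, state that the 12-month segment percentage will be reported with a two-sided 95% confidence interval that treats the participant as the cluster, and that this interval will be used when the result is set beside literature rates.

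One suitable method is a Wilson interval at n divided by the estimated design effect. The design effect comes from a participant-clustered variance with the G/(G − 1) correction and is not allowed below 1. If every segment fuses, the correlation cannot be estimated, so preset it at 1. On the base case that gives DEFF (30 + 40 × 2)/70 = 1.571, effective n 44.5 and a lower limit of 44.5/(44.5 + 3.84) = 92.1%. GEE with robust variance is an alternative when some segments fail, but the robust Wald interval covered only 90–94% in the simulation.

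In XIX.B, do the same for the 6- and 24-month rates, with a note that the interval covers sampling error only. The schedule in XIII.A has no CT at 6 months, and at 24 months CT is selective: "If clinically indicated, participants will complete a lumbar CT scan without contrast". The interval does not reflect that difference in imaging.

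The segment percentage stays the primary result. The percentage of participants with all treated segments fused, with an exact or Wilson interval, is an optional addition for use where a published rate is per participant.

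The cost is a short change of wording and a few lines of analysis on data already being collected. The result will look less precise than a bare percentage.

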### B. Study EndpointsN

X-rays as well as axial, coronal and sagittal CT reconstructions will be used to determine the presence of bridging bone in the posterolateral spine. The primary endpoint is treated segment fusion at 12 months post-operatively based on the following criteria:

- Presence of bridging trabecular bone; and
- < 5° Angular motion; and
- < 3 mm Translational motion.

Secondary evaluation parameters include:

1. The proportion of successfully fused treated segments 6 and 24 months postoperatively.
2. Improved postoperative pain, disability and physical-functioning scores compared to baseline values.
3. Overall satisfaction with the procedure.
4. The proportion of complications and adverse events.

---

N nanOss Bioactive 3D post-market study schedule of events

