#### ***F. Participant Disposition or Lost to Follow-Up***

It is expected that participants will complete the Study, and the PI will make every attempt to contact the participant to have the participant continue in the Study. If the participant is lost to follow up despite all attempts, the PI (or designee) will complete and sign the appropriate CRF.

The following are circumstances for which a participant would be identified as not continuing his or her participation in the Study:

- Lost to follow-up and no additional data is available on the participant's outcome.
- Participant died.

All information regarding the participant discontinuation in the Study will be recorded and includes:

- When the participant completes the Study.
- Indicates how the participant left the Study at their final visit.

For participants that are lost to follow-up, data from the visits that were completed will be used.

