#### ***G. Withdrawal criteria***

Participants will be advised that they may voluntarily withdraw from the Study at any time and will be instructed to notify the PI immediately. Participants may choose to withdraw for any reason and will be asked to reveal their reasons for withdrawal to the Sponsor.

A participant may be withdrawn from the Study without consent by the PI for any of the following reasons:

- The participant may relocate to another geographical area, which requires a change of the physician.
- The participant may be unable to continue participation in the Study due to some significant though unrelated condition or accident.
- The participant may be withdrawn from the Study by the PI or the Sponsor for noncompliance with the Study procedures.

All information regarding the participant discontinuation in the Study will be recorded and includes:

- When the participant completes the Study.
- Indicates how the participant left the Study at their final visit.

For participants that withdraw or are withdrawn, data from the visits that were completed will be used.

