### B. Qualitative Measurements

Qualitative assessments shall be performed by a single, independent radiographic reviewer that is board-certified, fellowship-trained, practicing neuro- or musculoskeletal radiologist. The following qualitative assessments shall be performed by a single, independent radiographic reviewer. The reviewer shall be a board-certified, fellowship-trained, practicing neuro- or musculoskeletal radiologist.

The qualitative assessments shall be conducted at the treated segments 6, 12 and 24 (as applicable) months postoperatively:

- Left & Right Posterolateral Bridging: X-rays as well as axial, coronal and sagittal CT reconstructions, when available, will be used to determine the presence of bridging. Assessment of bridging bone across the left and right posterolateral gutter, facet joint and/or transverse processes. Each treated segment will be graded separately. Posterolateral Bridging will be graded for each side (left and right) separately, and will include the entire posterolateral gutter, from the lateral-most aspect of the transverse processes to the medial-most aspects of the facet joints. Bridging between facet joints, between transverse processes, or between facet joint and transverse process will all be considered acceptable forms of bridging.
- Interbody Bridging: X-rays as well as axial, coronal and sagittal CT reconstructions,

when available, will be used to determine the presence of bridging. Assessment of bridging bone between the involved vertebral endplates. Each treated segment will be graded separately.

- Heterotopic Ossification
- Heterotopic bone formation will be evaluated to detect bone formation in unintended locations associated with the treatment.
- Hardware Condition: Assessment of device disassembly, loosening or fracture.
- Additional Observations: Other noteworthy observations will be documented at the radiologist's discretion.

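### A segment regrafted or refixated for non-union before the assessment can still be scored as fused, because fusion is defined by imaging alone

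*Combined protocol and SAP*

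**What the plan says.** Section XI.B introduces the endpoint: "The primary endpoint is treated segment fusion at 12 months post-operatively based on the following criteria". The criteria are bridging bone, angular motion below 5° and translational motion below 3 mm. Section XIX.A repeats them, accepts bridging on either side, and closes with: "Non-fusion will be defined as the failure to meet any one of the above criteria for fusion". Neither section mentions reoperation.

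Subsequent surgery appears elsewhere, always apart from fusion status:

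- Section XIX.B, item 6, is a secondary endpoint that includes "no device failure or subsequent intervention, excluding the removal of fixation after a solid fusion occurred".
- Section XIX.B also states: "The proportion of clinical complications, reoperations, revisions, as well as unexpected adverse events will be calculated".
- Section XIV makes later surgical interventions part of the safety assessment.

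Reoperation is not a listed ground for discontinuation (XII.F) or for withdrawal by the investigator (XII.G). The graft and hardware exclusions at the end of XII.E concern what is done at the study surgery, not at a later one.

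The study is uncontrolled (XI.A). Section X.B says: "The results of nanOss Bioactive 3D will be compared to those cited in literature".

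**The concern.** The study's purpose is to assess fusion with this graft mixed with autograft and marrow aspirate. If a segment fails to unite, is reoperated with new graft or fixation, and later shows bridging and little motion, its images reflect the second operation. Under the written definition the success is credited to the index graft.

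The event is foreseen. Section XVII.B names lack of solid fusion as the main risk of the product and also lists revision surgery. The plan guards against other fusion aids elsewhere: XII.E allows exclusion when other graft material is used posterolaterally at surgery, and XVI.F bars bone growth stimulators. It has no matching rule for graft or fixation added at a revision.

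At stake is the headline percentage. There is no concurrent arm scored by the same rule to offset the effect, and the documents do not say how the comparison literature scores revised segments.

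**Working it through.** The plan states no expected fusion rate, revision rate or sample-size calculation, so there is no figure of its own to reproduce. The check has four steps.

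**1. Follow one segment through the text.** Suppose a segment is revised for non-union at month 8 and meets all three criteria at the 12-month visit.

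- XII.F and XII.G: reoperation is not a listed reason to leave the study, so the participant stays in.
- XVI.G: visit windows run from the date of surgery, and nothing is said about a second operation.
- XIX.A: all three criteria are met, so the segment is fused.
- XIX.B: the reoperation is counted in item 6 and in the reoperation proportion; the segment remains fused.

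**2. Time available.** The 12- and 24-month visits may take place up to 8 weeks late (XVI.G), which is about 1.8 months.

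- Revision at month 8, 12-month visit: 12 − 8 = 4.0 months, up to 4.0 + 1.8 = 5.8 months.
- Revision at month 13, 24-month visit: 24 − 13 = 11.0 months, up to 11.0 + 1.8 = 12.8 months.

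XIX.B does not restate the fusion definition for 24 months, so the second line assumes that the same one is used.

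**3. Effect on the rate.** Let n be the segments in the denominator, F the number passing on imaging, and r the number of those F that were revised for non-union beforehand.

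- Written rule: F/n.
- Revised segments scored as non-fused: (F − r)/n.
- Difference: r/n, which is never negative.

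A revised segment with no usable images would also enter the second rate as non-fused, which lowers that rate further, so the direction does not change.

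The range of n follows from 50 expected participants (XII.C), at most 60 (XII.B), and one or two segments each (XII.D): 50 × 1 = 50 up to 60 × 2 = 120.

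| n | r = 0 | r = 1 | r = 2 |
|---|---|---|---|
| 50 | 0 | 2.0 points | 4.0 points |
| 100 | 0 | 1.0 | 2.0 |
| 120 | 0 | 0.8 | 1.7 |

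The values of r are assumptions. If 10% of segments could not be assessed, n would fall to 45 or 108, and one affected segment would add 1/45 = 2.2 or 1/108 = 0.9 points.

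**4. Side check on the denominator.** Let p be the fusion rate among assessable segments and m the fraction that cannot be assessed. Leaving the latter out, or counting them as non-fused, differs by p × m. With about 85% fused and 10% undetermined (both assumed), this is 38/45 = 84.4% against 38/50 = 76.0%, or 92/108 = 85.2% against 92/120 = 76.7%. Over assumed ranges of 70–95% and 5–20%, the gap runs from 0.70 × 0.05 = 3.5 points to 0.95 × 0.20 = 19 points. This shows why the denominator should be written down; it does not measure a bias.

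**The case against.** The strongest reply is that little is likely to happen at 12 months. The first scheduled imaging after discharge is by x-ray at 6 months. To be affected, a segment would usually have to be judged non-united after that, be revised, and then show bridging and pass both motion limits within a few months. Nothing in the documents supports a count above zero. The study is also descriptive, with no hypothesis test or success threshold for the rate to cross, and revisions are reported, so they are not hidden. All of this stands and limits the size of the point. It does not close the gap: the reported reoperations are not linked to the fusion status of the segment, and at 24 months the time constraint is much weaker.

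A second reply is that a revision-adjusted headline could be less comparable with the literature, whose scoring is not given. That is fair, and it is why the imaging-only rate should stay beside it.

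A reader might also infer that the handling of segments without usable 12-month images is wide open. The documents do not support that. XII.F says "For participants that are lost to follow-up, data from the visits that were completed will be used", and XII.G says "For participants that withdraw or are withdrawn, data from the visits that were completed will be used". Both point to available cases. XIX.A ties fusion to assessed images and promises the sample size with the percentage. Reading its non-fusion sentence as covering unimaged segments is possible but strained.

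Nor does XV.B show that the 12-month endpoint may be read without CT. Its sentence, "X-rays as well as axial, coronal and sagittal CT reconstructions, when available, will be used to determine the presence of bridging", covers three visits. No CT is scheduled at 6 months, and at 24 months it is conditional. At 12 months it is scheduled for everyone (XIII.A, XVI.G.2) and must be sent to the independent reviewer (XIII.E).

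**Conclusion.** The point holds for revised segments. As written, a treated segment that had posterolateral graft or fixation added or replaced for non-union before the assessment counts as fused if its later images pass. Against scoring it as non-fused, the direction is certain: the rate can only go up. The size is small and rests on an assumed count: with 0 to 2 affected segments, 0 to 4.0 points at 50 segments and 0 to 1.7 at 120. The 24-month effect also assumes that the 12-month definition carries over.

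The stronger conclusion, that the primary rate will be materially inflated, is not supported, because the documents give no revision rate and zero is possible. The denominator needs only a minor clarification: available cases is the natural reading, the incomplete or unreadable visit is not addressed, and the direction of any bias from unassessed segments is unknown.

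**What to change.** Add to XIX.A, for both 12 and 24 months:

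- A treated segment is scored as non-fused if, before that assessment, posterolateral graft or fixation was added or replaced at that segment for non-union. Removal of fixation after solid fusion does not count, in line with XIX.B item 6.
- The rate based on imaging alone is shown alongside.

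As a minor clarification in the same place: the denominator is treated segments whose fusion status can be determined (consistent with XII.F and XII.G), including those settled by the rule above. Report the number undetermined at 12 and 24 months, and give one sensitivity rate that counts them as non-fused.

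The cost is a few sentences, with no new visit, scan or procedure. Subsequent interventions are already collected under XIV. The complication form is a supplemental document not included here, so check that it records the segment, date and reason for each reoperation. The downside is that the headline fusion rate may be slightly lower.
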